4.4. Data Conventions

The precision of original measurements will be maintained in summaries, when possible.

Quantitative laboratory tests containing less than (<) and greater than (>) symbols are test results that are below and above quantifiable limits, respectively. In order to retain these values for analysis purpose, the numeric portion of the result will be imputed and stored within the analysis datasets.

4.5. Standard Calculations

Variables requiring calculation will be derived using the following formulas:

- Days – A duration expressed in days between one date (*date1*) and another later date (*date2*) will be calculated using the following formulas:
duration in days = $date2 - date1 + 1$, where $date1 \geq$ first infusion date
duration in days = $date2 - date1$, where $date1 <$ first infusion date
- Months – A duration expressed in months is calculated as the number of days divided by 30.4375
- Years – A duration expressed in years between one date (*date1*) and another date (*date2*) is calculated using the following formulas:
duration in years = $(date2 - date1 + 1)/365.25$, where $date1 \geq$ first infusion date
duration in years = $(date2 - date1)/365.25$, where $date1 <$ first infusion date

- Age – Age is calculated as the number of years from the date of birth (*DOB*) to the specified date, e.g., date of informed consent (*DOIC*):
$$\text{age (years)} = (\text{DOIC} - \text{DOB} + 1) / 365.25$$
- Height – Height entries made in inches (in) are converted to centimeters (cm) using the following formula:
$$\text{height (cm)} = \text{height (in)} \times 2.54$$
- Weight – Weight entries made in pounds (lb) are converted to kilograms (kg) using the following formula:
$$\text{weight (kg)} = \text{weight (lb)} / 2.2046$$
- Temperature – Temperature entries in degrees Fahrenheit are converted to degrees Celsius using the following formula:
$$\text{temp (degrees Celsius)} = 5 / 9 \times (\text{temp [degrees Fahrenheit]} - 32)$$
- Body Mass Index (BMI) – BMI is calculated using height (cm) and weight (kg) using the following formula:
$$\text{BMI (kg/m}^2\text{)} = \text{weight (kg)} / ([\text{height (cm)} / 100]^2)$$
- Change from baseline – Change from baseline will be calculated as:
$$\text{Change} = \text{post baseline value} - \text{baseline value}$$
- Percent change from baseline – Change from baseline will be calculated as:
$$\text{Percent change from baseline} = ([\text{post baseline value} - \text{baseline value}] / \text{baseline value}) \times 100$$

4.6. Analysis Visit Windows

Each visit will be denoted by its “month” and “day” such that the first dose day is denoted as Month 1-Day 1; subsequent months will use sequential numbers (e.g., the second dose is administered on Month 2-Day 1). Each infusion is scheduled to be 28 days from the previous infusion (± 2 days for Months 2 and 3; ± 5 days for Months 4 and beyond).

“Cycle” is reserved to denote administration of chemotherapy. It is expected that all visits should occur according to the protocol schedule.

In data listings, the relative study day from first infusion of all dates will be presented.

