Peripheral Neuropathy Assessment ⁹	X	X	Every 3 months ¹⁰	X
SF-36 Health Survey ¹¹	X	X	Every 6 months ¹²	X
6MWT ¹³	X ¹⁴	X ¹⁴	Every 6 months ¹²	X
Echocardiogram		X	Every 12 months ¹⁵	X ¹⁶
ECG (12-lead in triplicate; local)	X	X	Every 3 months ^{10,17}	X
Vital Status Telephone Call				Every 3 months ¹⁸
Laboratory²¹				
Hematology & Chemistry ¹⁹	X	X	X	X
Amylase	X	X	X	X
Coagulation ²⁰	X	X	X	X
Troponin T	X	X	X	X
NT-proBNP ¹³	X	X	X	X
Pregnancy (WOCBP) ²²	X	X	X	X, X ²³
Serum Free Light Chain		X	Every 3 months ¹⁰	X
SPEP & 24-hour UPEP ²⁴		X	Every 3 months ^{10,25}	X
SIFE & UIFE		X	Every 3 months ^{10,25}	X
Urinalysis (dip stick) ²⁶		X	Every 3 months ¹⁰	X
24-hr Urine Protein Excretion ²⁴		X	Every 3 months ¹⁰	X
Other				
Serum NEOD001 Sample ²⁷	X	X	Every 3 months ¹⁰	X
Serum anti-NEOD001 Antibody Sample ²⁸	X	X	Every 3 months ¹⁰	X
NEOD001 Infusion ²⁹			X	

ECG = electrocardiogram; ECOG PS = Eastern Cooperative Oncology Group performance status; EOI = end of infusion; EOS = End of Study; INR = international normalized ratio; NT-proBNP = N-terminal pro B-type natriuretic peptide; NYHA = New York Heart Association; PK = pharmacokinetic; PT = prothrombin time; PTT = partial thromboplastin time; SF-36 = Short form-36; SIFE = serum immunofixation electrophoresis; 6MWT = 6-Minute Walk Test; SPEP = serum protein electrophoresis; UIFE = urine immunofixation electrophoresis; UPEP = urine protein electrophoresis; WOCBP = women of childbearing potential.

1. Rescreening is allowed once per subject. Only repeat tests that did not meet eligibility requirements.
2. Day 1 assessments may be conducted ±5 days from Day 1, with the exception of Month 1-Day 1 (i.e., no window is allowed at Month 1).

3. Conduct the EOS Visit 30 (± 5) days after last administration of study drug. Two additional evaluations are to be conducted beyond this time point, see Footnotes 18 and 23.
4. Obtain medical history since subject's last visit in Study NEOD001-001 (including all major hospitalizations and surgeries), as well as the subject's current medical status and prior therapies for AL amyloidosis. Adverse events that resolved prior to the subject's last visit in Study NEOD001-001 and prior to signing the ICF for this study should be assessed as possible medical history in this study.

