5. Record all prior therapies for AL amyloidosis taken prior to signing ICF for this study and since last visit in Study NEOD001-001. Record all prior/concomitant medications taken or received by a subject within the 28 days prior to the Month 1-Day 1 Visit through the EOS Visit, and any changes to concomitant medications during the study. See Study Manual for more information.
6. Adverse events will be collected from the time that the informed consent form is signed through 30 days after the last dose of study drug or last study visit, whichever is later. Record any adverse events that were ongoing from the subject's last visit in Study NEOD001-001 and at the time of the NEOD001-OLE001 Screening Visit.
7. Physical examination will include weight, height (Screening only), and examination of the following: general appearance; head, ears, eyes, nose, and throat; neck; skin; cardiovascular system; respiratory system; abdominal system; and nervous system. A complete physical examination will be done at Screening and EOS; at all other visits, the components of the physical examination will be as clinically indicated. However, at all time points the following should be assessed: macroglossia, submandibular nodes/fullness, adenopathy, ecchymoses, liver/spleen size (palpable +/-), ascites (+/-), and edema (which should be quantified on a scale of 0-4).
8. Vital signs include heart rate (HR), blood pressure (BP), respiratory rate (RR), and body temperature; assess per Section 6.3.2. **Month 1-Day 1:** Predose, halfway through infusion, immediately at EOI (+5 minutes), and 30 (± 5) minutes and 60 (± 10) minutes after EOI. **All Other Months-Day 1:** Predose, EOI (+5 minutes), and 60 (± 10) minutes after EOI.
9. Peripheral neuropathy assessment: only for subjects previously enrolled in Cohort C of Study NEOD001-001.
10. Perform every 3 months (Months 3, 6, 9, 12, etc.).
11. Administer SF-36 before performing any other study assessments on the day it is administered (Appendix 2).
12. Perform every 6 months (Months 6, 12, 18, etc.).
13. NT-proBNP must be drawn before conducting 6MWT, if performed on the same calendar day. Collect blood pressure and heart rate pre- and post-6MWT administration.
14. Two pretreatment 6MWTs are required before the first administration of study drug, with a minimum of 4 days in between the two tests. The second test must be completed 1 to 2 days before the Month 1-Day 1 Visit.

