15. Echocardiogram to be conducted every 12 months and may be conducted within 10 days before the visit.
16. Repeat echocardiogram at EOS if not performed within 60 days prior to visit.
17. For all post-Screening visits, ECGs are to be performed predose and within 15 minutes after the EOI.
18. Conduct telephone call approximately 3 months after subject's last study visit and approximately every 3 months thereafter for up to 5 years, death, or subject withdraws consent, whichever occurs first.
19. Hematology and chemistry per Appendix 3. At Screening, include Screen for Infectious Diseases per Appendix 3. Within 3 days before the first day of a new regimen of chemotherapy, conduct an unscheduled central laboratory collection (including hematology, chemistry, PT/INR, and PTT).
20. Coagulation per Appendix 3. Collect unscheduled citrated plasma samples for subjects with relevant serious adverse event(s); if defects are identified, additional analytes will be analyzed, as indicated (see Appendix 4).
21. All laboratory tests to be done centrally, unless otherwise noted.
22. Perform pregnancy tests for WOCBP as follows: **Screening:** serum test (central) within 28 days before Month 1-Day 1; **Monthly starting with Month 2:** urine test (local) predose; **EOS:** serum test (central). A positive urine pregnancy test (local laboratory) is to be confirmed with a serum pregnancy test (central laboratory).
23. Perform serum pregnancy test (local; WOCBP only) 90 (± 5) days after the last study drug administration.
24. Begin urine collections 24 hours prior to the study visit.
25. After Baseline, use to confirm initial within-study hematologic complete response only.
26. Urinalysis per Appendix 3.
27. NEOD001 serum samples (for population PK analysis): collect predose, at EOI (record the time, but the sample can be collected at any time after the infusion on Day 1), and at other times as clinically indicated, such as when significant toxicity occurs.
28. Anti-NEOD001 antibody samples: collect predose and at other times as clinically indicated, such as when significant toxicity occurs.

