4.6.1. NEOD001 Therapy Visit Windows

Table 2 defines the visit windows for assessments taken at 1-month intervals to be established with respect to relative day from the start of NEOD001 therapy.

Table 2: NEOD001 Therapy 1-Month Interval Visit Windows (Days)

Months	Target Study Day ^a	Analysis Window Study Day ^a	
		Low	High
NEOD001 Baseline ^b	1	Closest visit to Day 1, prior to first NEOD001 dose	
NEOD001 Month 1	28	2	42 [= 28 + 28/2]
NEOD001 Month 2	56	43 [= (28 + 28/2 + 1)]	70 [= 56 + 28/2]
NEOD001 Month x	28*x	(x-1)*28 + 28/2 + 1	x*28 + 28/2

^a Study day will be calculated from first dose date according to Section 2.2.4.1.

^b NEOD001 Baseline is defined in Section 2.2.4.1.

Table 3 defines the visit windows for assessments taken at 3-month intervals to be established with respect to relative day from the start of NEOD001 therapy.

Table 3: NEOD001 Therapy 3-Month Interval Visit Windows (Days)

Months	Target Study Day ^a	Analysis Window Study Day ^a	
		Low	High
NEOD001 Baseline ^b	1	Closest visit to Day 1, prior to first NEOD001 dose	
NEOD001 Month 3	84	2	126 [= 84 + 84/2]
NEOD001 Month 6	168	127 [= (84 + 84/2) + 1]	210 [= (168 + 84/2)]
NEOD001 Month x	28*x	(x-3)*28 + 84/2 + 1	x*28 + 84/2

^a Study day will be calculated from first dose date according to Section 2.2.4.1.

^b NEOD001 Baseline is defined in Section 2.2.4.1.

The duration of 60 days between the time from last dose in the original parent study (NEOD001-001) to first dose in the OLE was chosen based on PK experience of elimination of study drug.

Note that the assessment used in the analyses is chosen step by step as follows in cases when multiple records exist within the same analysis window:

1. Choose the assessments with shortest distance from the target day.
2. If multiple assessments are the same distance from the target day for a particular analysis window, the later assessments are chosen.
3. If there are 2 or more assessments taken on the same date or same date and time, the rules for choosing the assessment are:
 - a. First take the assessment from the scheduled visit, then take the assessment from the re-test visit (applicable to laboratory tests), then take the assessment from the discontinuation visit, then take the assessment from the unscheduled visit.
 - b. Take the assessment with the most abnormal value.
 - Most abnormal value is determined by taking the value that is the further from the lower limit of normal (LLN) or ULN.

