9.3.1. Serum Chemistry, Hematology, and Coagulation

Quantitative serum chemistry, hematology, and coagulation results will be summarized using descriptive statistics at OLE baseline, each post OLE baseline visit, minimum OLE value, and maximum OLE value. The change and percentage change from OLE baseline will also be summarized.

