9.6. Electrocardiograms

ECGs measurements will be made in triplicate, 5 to 10 minutes apart and assessed by a central reader. For summary purposes, the mean of the three measurements will be used. ECG parameters including, time between 2 consecutive R waves [RR], PR interval, QRS duration, QT (uncorrected) interval, QT interval corrected by the Bazett's formula [QTcB], and QT interval corrected by the Fridericia's formula [QTcF], will be summarized using descriptive statistics will be presented for observed values, change from NEOD001 baseline, change from OLE baseline, at each NEOD001 post-baseline time point, and at each OLE post-baseline time point.

A categorical summary of the following abnormal maximum mean triplicate QTcF values will be presented: >450 msec, >480 msec, and >500 msec. Change from NEOD001 baseline and OLE baseline summaries will also be presented for measurements that represent a change from baseline >30 msec and >60 msec. Three separate listings for those subjects with any QTcF >450 msec or a QTcF change from either baseline >30 msec, any QTcF >480 msec or a QTcF change from either baseline >30 msec, and any QTcF >500 msec or a QTcF change from baseline >60 msec will be presented. The observation(s) meeting criteria for inclusion will be flagged in the listing.

Overall interpretation results for ECGs and the investigator interpretation results are collected as normal, abnormal not clinically significant, and abnormal clinically significant. Subjects whose interpretation shifts from normal to abnormal clinically significant or not clinically significant will be listed separately including description of the abnormality and any associated comments.

All ECG results will be presented in by-subject data listings.

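### The OLE analysis windows are targeted 27 days after the visits they are named for, so one visit carries two month numbers and an End of Study ECG can replace the scheduled quarterly ECG

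*SAP*

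**What the plan says.** **Visit names.** SAP 4.6 numbers visits by dose: the first dose day is Month 1-Day 1, and "subsequent months will use sequential numbers (e.g., the second dose is administered on Month 2-Day 1". Infusions are scheduled 28 days after the previous one. SAP 4.1 makes the first OLE dose Day 1.

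**Windows.** SAP 4.6.2 counts study day from the first OLE dose and sets the target for OLE Month x at Day 28x in both tables. Table 4 (monthly assessments) allows 14 days above the target and Table 5 (3-monthly assessments) allows 42. Neither has an EOS row.

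**Choosing among records.** Section 4.6.2 adopts the rules of 4.6.1. Rule 1 is "Choose the assessments with shortest distance from the target day". Rule 2 gives ties to the later record. Rule 3 ranks scheduled visits above discontinuation visits, but applies only in this case: "If there are 2 or more assessments taken on the same date or same date and time".

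**Schedule.** Protocol Table 1 requires ECGs quarterly (footnote 10: "Perform every 3 months (Months 3, 6, 9, 12, etc") and at EOS, which is 30 (±5) "days after last administration of study drug" (footnote 3). Footnote 17 adds: "For all post-Screening visits, ECGs are to be performed predose and within 15 minutes after the EOI".

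**Reporting.** Laboratory results "will be summarized using descriptive statistics at OLE baseline, each post OLE baseline visit, minimum OLE value, and maximum OLE value" (SAP 9.3.1). ECG parameters are summarised "at each OLE post-baseline time point" (SAP 9.6). SAP 2.3.1 lists changes in laboratory values, vital signs and ECGs among the primary endpoints.

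**The concern.** Adjoining sections of the SAP use two conventions for the word Month. Section 4.6 counts doses, starting at 1 on the first dose day. The windows count 28-day periods completed since that day. The gap is almost a full dosing interval, so it matters which window width is applied: the narrow monthly windows move a visit to the previous number, and the wide quarterly windows do not.

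Two things are at stake in the by-visit tables for primary safety endpoints. A reader cannot match a laboratory or vital-sign row to the ECG row with the same month number. In addition, the quarterly target lies close to where EOS falls after a quarterly dose, so nearest-to-target selection favours EOS over the scheduled ECG.

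**Working it through.** **Reproducing the SAP's limits.** Table 4, Month x: 28(x−1)+15 to 28x+14. This gives Month 1 high = 42 and Month 2 = 43–70. Table 5, Month x: 28(x−3)+43 to 28x+42. This gives Month 3 high = 126 and Month 6 = 127–210. All match the printed tables.

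**Offset.** Nominal day of the Month m visit = 1 + 28(m−1) = 28m−27. Target for Month m = 28m. Difference = 27 days for every m.

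**Labels on nominal timing.**

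| Visit | Day | Table 4 label (window) | Table 5 label (window) |
|---|---|---|---|
| Month 3 | 57 | Month 2 (43–70) | Month 3 (2–126) |
| Month 6 | 141 | Month 5 (127–154) | Month 6 (127–210) |
| Month 36 | 981 | Month 35 (967–994) | Month 36 (967–1050) |

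Across Months 2 to 36, 35 of 35 monthly visits get label m−1 in Table 4, and 12 of 12 quarterly visits get label m in Table 5. For an on-schedule completer, the Table 4 row for OLE Month 36 (995–1022) holds only EOS (981+25 to 981+35 = Days 1006–1016).

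**Drift.** Let D be the cumulative shift of a visit from its nominal day. Table 4 gives m−1 for D = −14 to +13, and Table 5 gives m for D = −14 to +69. The two labels therefore differ throughout −14 to +13. From +14 to +41 Table 4 also gives m, and the labels agree.

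**EOS against the scheduled ECG, last dose at a quarterly month x.** With a gap g of 25 to 35 days, nominal EOS is Day 28x−27+g, that is 28x−2 to 28x+8. It is 0 to 8 days from target, against 27 for the scheduled ECG. EOS is selected in all 132 combinations (12 last-dose months × 11 gaps). At Month 36 the target is Day 1008: the scheduled ECG on Day 981 is 27 days off and EOS on Day 1011 (g = 30) is 3 days off.

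With drift at Month 36, the scheduled distance is |27−D| and the EOS distance is |D+g−27|. EOS wins when D ≤ (54−g)/2:
- g = 25: up to +14 days
- g = 30: up to +12 days
- g = 35: up to +9 days

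If every dose stays within 5 days of its nominal day, the scheduled ECG is 22–32 days off and EOS 0–13, so EOS always wins.

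**Other last-dose months (nominal timing).**
- Months 4, 7, …, 34: EOS is 26–36 days from the target of the preceding quarterly row, against 27. It wins only at g = 25 (26 v 27) or g = 26 (27 v 27, tie to the later record): 22 of 121 combinations (11 months × 11 gaps).
- Months 5, 8, …, 35: EOS displaces nothing but is alone in the next quarterly row. With the last dose at Month 8 (Day 197), EOS on Day 227 falls in OLE Month 9 (211–294), a visit the subject never reached.

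**The case against.** The strongest reply is that Table 4 is sound if OLE Month is read as elapsed 28-day months: Day 141 is 140 days, or five such months, after the first dose, and each nominal visit is 1 day from a target. That is true of Table 4 alone. Quarterly visits occur after 2, 5, 8, … elapsed months, so the same reading fails in Table 5. No single reading fits both tables.

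A second reply is that a predose ECG is itself about 28 days after the preceding infusion, so an EOS ECG at about 30 days is a similar end-of-interval reading. The SAP's own treatment-emergent period also runs at least 30 days past the last dose. This limits the clinical difference if predose and post-infusion ECGs are handled as separate time points, because then only the predose record is displaced. The SAP does not say they are. If they are pooled, the post-infusion record can be lost as well.

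Third, intervals run from the previous infusion, so lateness can accumulate. Fifteen days over 35 intervals (15/35 = 0.43 day per dose) ends the displacement at Month 36 for all gaps from 25 to 35 days and brings the two labels into agreement. That stands as a limit on how many subjects are affected, and the documents do not give those numbers.

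Fourth, Tables 2 and 3 use the same 28x formula. Changing only Tables 4 and 5 would create a new mismatch in the vital-sign and ECG summaries that use both baselines. This is a fair point about how to make the fix.

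**Conclusion.** The windows are wrong as written and should be corrected. The 27-day offset is exact. The label mismatch holds for every quarterly visit while cumulative drift is between −14 and +13 days. EOS displaces the scheduled ECG for any subject whose last dose is at a quarterly month with dosing near schedule, including every on-schedule 36-month completer. These results assume that EOS records enter the windows. Nothing in the SAP exempts them, and rule 3 names the discontinuation visit.

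The reach is limited to descriptive by-visit summaries, at most one displaced quarterly ECG row per subject, and no inferential test is planned. Adverse event tables, laboratory minimum and maximum values, worst-grade shifts and maximum-QTcF categories do not change. Listings still show study day.

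**What to change.** 1. In Tables 4 and 5, set the Month x target at Day 28(x−1)+1.
   - Monthly: Month 2 = 2–43, Month 3 = 44–71, Month x = 28(x−2)+16 to 28(x−1)+15.
   - 3-monthly: Month 3 = 2–99, Month 6 = 100–183, Month x = 28(x−4)+44 to 28(x−1)+43.
2. Give EOS its own analysis visit, outside the on-treatment windows. Re-centring alone removes the nominal-timing displacement (0 of 374 combinations: 34 last-dose months × 11 gaps). It would still leave EOS alone in an unreached row: with the last dose at Month 35 (Day 953), EOS on Days 978–988 falls in the new Month 36 window, 940–1023.
3. State whether predose and post-infusion ECGs are separate time points.
4. Optionally, prefer scheduled over unscheduled records before applying nearest-to-target. Steps 1 and 2 do not depend on this.
5. Check Tables 2 and 3 against the parent-study visit schedule, which these documents do not give, and align them in the same SAP revision.

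The cost is edits to two tables, one EOS row and a line or two of rules, plus the check of Tables 2 and 3. No new data are needed.

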4.6.1. NEOD001 Therapy Visit Windows

Table 2 defines the visit windows for assessments taken at 1-month intervals to be established with respect to relative day from the start of NEOD001 therapy.

Table 2: NEOD001 Therapy 1-Month Interval Visit Windows (Days)

Months	Target Study Day ^a	Analysis Window Study Day ^a	
		Low	High
NEOD001 Baseline ^b	1	Closest visit to Day 1, prior to first NEOD001 dose	
NEOD001 Month 1	28	2	42 [= 28 + 28/2]
NEOD001 Month 2	56	43 [= (28 + 28/2 + 1)]	70 [= 56 + 28/2]
NEOD001 Month x	28*x	(x-1)*28 + 28/2 + 1	x*28 + 28/2

^a Study day will be calculated from first dose date according to Section 2.2.4.1.

^b NEOD001 Baseline is defined in Section 2.2.4.1.

Table 3 defines the visit windows for assessments taken at 3-month intervals to be established with respect to relative day from the start of NEOD001 therapy.

Table 3: NEOD001 Therapy 3-Month Interval Visit Windows (Days)

Months	Target Study Day ^a	Analysis Window Study Day ^a	
		Low	High
NEOD001 Baseline ^b	1	Closest visit to Day 1, prior to first NEOD001 dose	
NEOD001 Month 3	84	2	126 [= 84 + 84/2]
NEOD001 Month 6	168	127 [= (84 + 84/2) + 1]	210 [= (168 + 84/2)]
NEOD001 Month x	28*x	(x-3)*28 + 84/2 + 1	x*28 + 84/2

^a Study day will be calculated from first dose date according to Section 2.2.4.1.

^b NEOD001 Baseline is defined in Section 2.2.4.1.

The duration of 60 days between the time from last dose in the original parent study (NEOD001-001) to first dose in the OLE was chosen based on PK experience of elimination of study drug.

Note that the assessment used in the analyses is chosen step by step as follows in cases when multiple records exist within the same analysis window:

1. Choose the assessments with shortest distance from the target day.
2. If multiple assessments are the same distance from the target day for a particular analysis window, the later assessments are chosen.
3. If there are 2 or more assessments taken on the same date or same date and time, the rules for choosing the assessment are:
 - a. First take the assessment from the scheduled visit, then take the assessment from the re-test visit (applicable to laboratory tests), then take the assessment from the discontinuation visit, then take the assessment from the unscheduled visit.
 - b. Take the assessment with the most abnormal value.
 - Most abnormal value is determined by taking the value that is the further from the lower limit of normal (LLN) or ULN.

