4.6.2. OLE Therapy Visit Windows

Table 4 defines the visit windows for assessments taken at 1-month intervals to be established with respect to relative day from the start of NEOD001 therapy in the OLE.

Table 4: OLE Therapy 1-Month Interval Visit Windows (Days)

Months	Target Study Day ^a	Analysis Window Study Day ^a	
		Low	High
OLE Baseline ^b	1	Closest visit to Day 1, prior to first OLE NEOD001 dose	
OLE Month 1	28	2	42 [= 28 + 28/2]
OLE Month 2	56	43 [= (28 + 28/2) + 1]	70 [= 56 + 28/2]
OLE Month x	28*x	$(x-1)*28 + 28/2 + 1$	$x*28 + 28/2$

OLE = open-label extension.

^a Study day will be calculated from first OLE dose date.

^b OLE Baseline is defined in Section 2.2.4.2.

Table 5 defines the visit windows for assessments taken at 3-month intervals to be established with respect to relative day from the start of NEOD001 therapy in the OLE.

Table 5: OLE Therapy 3-Month Interval Visit Windows (Days)

Months	Target Study Day ^a	Analysis Window Study Day ^a	
		Low	High
OLE Baseline ^b	1	Closest visit to Day 1, prior to first OLE NEOD001 dose	
OLE Month 3	84	2	126 [= 84 + 84/2]
OLE Month 6	168	127 [= (84 + 84/2) + 1]	210 [= (168 + 84/2)]
OLE Month x	28*x	$(x-3)*28 + 84/2 + 1$	$x*28 + 84/2$

OLE = open-label extension.

^a Study day will be calculated from first OLE dose date.

^b OLE Baseline is defined in Section 2.2.4.2.

Note that same scheme will be applied as described Section 4.6.1 when multiple records exist within the same analysis window.

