9.5. Vital Signs

Vital sign parameters including temperature (C), systolic and diastolic pressure (mmHg), pulse (beats/min), and respiratory rate (breaths/min) will be presented in a data listing. Method of collection will be provided in the listing; however, summaries will be generated without regard to the method of collection. Summaries of vital sign parameter results, change from NEOD001 baseline, change from OLE baseline, percent change from NEOD001 baseline, and percent change from OLE baseline, will be summarized using descriptive statistics at baseline and at each post-baseline visit. In addition, change and percent change from baseline will be presented from pre-dose to post-dose at infusion visit.

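### The same-date record rule can make the by-visit vital-sign value a selected extreme, or a post-infusion reading, set against an unselected pre-infusion baseline

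*SAP*

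**What the plan says.** SAP 4.6.1 gives an ordered rule for windows that hold more than one record.

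- Step 1 takes the record closest to the target day.
- Step 2: "If multiple assessments are the same distance from the target day for a particular analysis window, the later assessments are chosen".
- Step 3 opens with "If there are 2 or more assessments taken on the same date or same date and time". Step 3a ranks records by visit type: scheduled, re-test, discontinuation, unscheduled. Step 3b is "Take the assessment with the most abnormal value", with the definition "Most abnormal value is determined by taking the value that is the further from the lower limit of normal (LLN) or ULN".

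SAP 4.6.2 carries the rule to the extension: "Note that same scheme will be applied as described Section 4.6.1 when multiple records exist within the same analysis window".

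On infusion days from Month 2, Protocol Table 1, footnote 8 (repeated in SAP Table 1) schedules vital signs "Predose, EOI (+5 minutes), and 60" (±10) minutes after the end of infusion, which is three sets. Month 1-Day 1 has five.

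SAP 9.5 says that vital-sign results and changes from both baselines "will be summarized using descriptive statistics at baseline and at each post-baseline visit". It then adds a pre-dose to post-dose summary at infusion visits. SAP 2.2.4.2 defines the OLE baseline for vital signs as the last assessment before the first OLE infusion. SAP 2.3.1 lists change in vital signs among the primary endpoints.

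**The concern.** The three readings of an infusion day share a date and all belong to the scheduled visit. Step 3a cannot separate them, so step 3b decides. It chooses among readings before and after infusion by how abnormal they look, whereas baseline is a pre-infusion reading chosen without regard to its value. Selection on one side only widens the distribution of change even if nothing has changed. If the population sits off the middle of the range, it also moves the mean. There is no control arm in which the same distortion would appear.

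The SAP also leaves the rule incomplete for vital signs. It supplies fallback limits only for INR and eGFR (SAP 9.3), and distance from a limit is not the same as distance outside the range. A programmer would have to settle both points with open-label data in hand.

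**Working it through.** The plan states no figure on this point, so there is none to reproduce. The check has two parts.

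**1. Which records reach step 3b**

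The window for Month x has its target at Day 28x and, after the first, runs from 28(x−1)+15 to 28x+14. This gives Days 2–42 for Month 1 and 43–70 for Month 2, as printed. Infusions fall nominally on Day 1+28(k−1), that is Days 1, 29, 57, and so on.

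- Month 1-Day 1 is Day 1, before the first OLE window opens on Day 2. The five readings of that day do not enter an OLE post-baseline window, so the number that matters there is three.
- Infusion on Day 29 against target Day 28 is a distance of 1. A reading on Day 28 has distance 0 and wins under step 1. Protocol 6.1.2 asks for pre-infusion assessments 1 to 2 days ahead, so this can happen.
- A reading on Day 27 also has distance 1. Step 2 then takes the later date, Day 29, and its three readings go to step 3. Choosing between days is thus a natural task for step 2.

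**2. Size of the effect**

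None of these inputs is in the documents; all are assumed: systolic limits 90 and 140 mmHg; between-subject SD 12 (population mean 105) or 15 (means 115 and 125); day-to-day SD 6; within-day SD 6; no true change; three exchangeable readings; 400,000 simulated subjects.

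Step 3b has more than one possible meaning.

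- *Reading A*, the larger of the two distances: max(|x−90|, |x−140|) = |x−115| + 25. This picks the reading furthest from mid-range.
- *Reading B*, furthest outside the limits, and predose if none is outside.
- The distance to the nearer limit would reverse the intent. For readings of 115 and 140, neither outside the limits, the nearer-limit distances are 25 and 0, so 115 is chosen. The larger distances are 25 and 50, so reading A chooses 140.

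Analytic check of the simulation: the SD of predose change is √(2×6² + 2×6²) = √144 = 12.0, and the SD for the mean of three readings is √(2×6² + 6² + 6²/3) = √120 = 10.95. The simulation gave 11.98–12.00 and 10.94–10.98.

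| Population mean | Predose: mean change (SD) | A: mean change (SD) | B: mean change (SD) |
|---|---|---|---|
| 105 | 0.0 (12.0) | −2.7 (13.0) | −1.3 (12.6) |
| 115 | 0.0 (12.0) | 0.0 (13.3) | 0.0 (12.6) |
| 125 | 0.0 (12.0) | +2.3 (13.0) | +1.3 (12.6) |

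The selected record is the predose one in about 33% of cases under A. At population mean 105, varying the within-day SD gives:

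| Within-day SD | Predose SD | A: mean change (SD) | B: mean change (SD) |
|---|---|---|---|
| 4 | 10.19 | −1.84 (10.84) | −0.72 (10.55) |
| 10 | 16.50 | −4.26 (18.32) | −2.85 (17.89) |

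If step 2 is taken to decide, the 60-minute reading is used. With no true change it gives mean 0.0 and SD 12.0, so there is no inflation. With an assumed post-infusion dip of 5 mmHg and population mean 115, the by-visit mean change is −5.0 from the 60-minute reading, −4.2 under A, −1.6 under B and 0.0 from the predose reading. A transient infusion effect would then appear as change between visits.

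**The case against.** The strongest reply is that step 3b cannot be executed for vital signs, because it is defined by limits that the SAP does not supply for them. On that view the defect is an unspecified record rather than a chosen extreme. This stands in part: a reader might infer that by-visit change is certainly built from extremes, and the text does not establish that. It does not clear the plan, because 4.6.1 is worded generally and only its re-test clause is tied to laboratory tests.

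Step 2 could also be held to settle same-day ties in favour of the 60-minute reading. That leaves the same-date wording of step 3 with little to do, and it still sets a post-infusion value against a pre-infusion baseline. Step 1 does pre-empt the tie, but only where a reading on another day is closer to target.

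SAP 9.5 does have a pre-dose to post-dose summary, so infusion-related change is not lost. That table is additional, however, and does not define the by-visit record.

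A reader might extend the point to ECGs. SAP 9.6 already averages the triplicate and reports by time point. All that remains is that predose and post-infusion ECGs share a date (Protocol Table 1, footnote 17).

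A reader might also count subjects whose change passes a fixed threshold, or quote shifts for subjects with high or low true means. SAP 9.5 plans neither table and SAP 6 plans no subgroups. Over a mid-range population the opposing shifts cancel.

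**Conclusion.** The concern holds as a minor defect confined to the by-visit vital-sign summaries. As written, the by-visit value can be the most abnormal of three same-day readings, or the 60-minute reading, against an unselected pre-infusion baseline. The main effect is on spread: the SD of change rises from about 12.0 to 12.6–13.3 mmHg under the assumed limits and a within-day SD of 6, with more extreme minimum and maximum values. SAP 4.1 plans to print these statistics. The mean shift is near 0 when the population mean is mid-range and up to about 2.7 mmHg when it is 10 mmHg off.

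These sizes rest on assumed limits and SDs, exchangeable readings and no true change. That selection on one side widens the spread does not depend on the particular values. The documents do not support a claim that mean change is necessarily biased, or that five readings at Month 1-Day 1 feed the OLE post-baseline summaries. The consequence is limited: SAP 9 plans no inferential safety comparison unless otherwise specified, the study has one arm, and every reading stays in the listings.

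**What to change.** Two sentences in the SAP.

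1. In 4.6.1 or 9.5: by-visit change in vital signs uses the predose reading of the infusion visit, and end-of-infusion and 60-minute readings are summarised separately by nominal time. Steps 1 and 2 would still choose the visit.
2. In 4.6.1: step 3b applies only to true duplicate laboratory results and takes the value furthest outside the normal range or, if none is outside, the later value.

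For ECGs, state only whether the by-visit summary uses the predose or the post-infusion triplicate mean; the averaging rule needs no change.

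No new data are needed. SAP 4.3 already relies on vital-sign times labelled as before and immediately after infusion, so the readings can be told apart. The cost is the wording and the matching derivation in the analysis datasets.
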